6.5. Confirmatory Visit

Subjects with HCV RNA \geq LLOQ at either post-treatment Week 4 or 12 visits will be asked to return for confirmatory visit within 2 weeks. A sample for viral HCV RNA sequencing/phenotyping will be collected.

6.6. End of Study

Discontinuation from study drug dosing and discontinuation from the overall study, including the Post-treatment period, will be collected as two separate events.

The end of study will occur at the post-treatment Week 4 visit in the case of subjects who do not achieve SVR4, and the post-treatment Week 12 visit in the case of patients who do achieve SVR4.

6.7. Procedures and Specifications

6.7.1. Clinical Laboratory Analytes

Hematology: Hematocrit, Hemoglobin (Hb), Platelet count, Red blood cell count (RBC), White blood cell count (WBC) with differential (absolute and percentage) including Lymphocytes, Monocytes, Neutrophils, Eosinophils, Basophils, Reticulocyte count and mean corpuscular volume (MCV).

Coagulation: international normalized ratio (INR), Prothrombin time (PT), Activated partial thromboplastin time (APTT).

Chemistry: Alanine aminotransferase (ALT/SGPT), Aspartate aminotransferase (AST/SGOT), Albumin, Alkaline phosphatase, Creatine Kinase (CK), Creatinine, Total Bilirubin (reflex to Direct Bilirubin), Glucose, Lipase, Potassium, Sodium, Uric Acid, Fibrotest®/APRI calculation and Direct Bilirubin at Screening only.

Virological Tests: Serologies for HCV and HBV, Serology and/or antigen testing for HIV, including reflex testing, as necessary. HCV RNA will be measured using the COBAS® AmpliPrep®/COBAS® TaqMan® HCV Quantitative Test, v2. HCV genotype and subtype will be determined using the Siemens VERSANT® HCV genotype INNO-LiPA 2.0 Assay. HIV RNA will be measured using the AmpliPrep/COBAS® TaqMan® HIV-1 Test, v2.0. If HIV-1 virologic rebound is confirmed, HIV-1 genotype/phenotype will be determined using the PhenoSense™ Integrase HIV, GeneSeq™ Integrase HIV, PhenoSense™ HIV, GenoSure MG, GeneSeq™ HIV, and PhenoSense GT™. Gilead reserves the right to use alternate assays for HCV RNA, HIV RNA, HCV genotype, and HIV-1 genotype/phenotype should the above assays become unavailable or the results are indefinite.

IL28B genotype will be determined by polymerase chain reaction (PCR) amplification of the SNP, rs12979860, with sequence specific forward and reverse primers and allele specific fluorescently labeled TaqMan® MGB probes. Gilead reserves the rights to use an alternate assay for IL28B determination should the above assay become unavailable.

Pregnancy Tests: Serum β -hCG or Urine β -hCG (if positive, requires immediate confirmation with Serum β -hCG)

Additional Tests: Urine Drug screen (for Amphetamines, Cocaine, Methadone, Opiates) and Hemoglobin A1c (HbA1c), CD4 T-lymphocyte Absolute Count and %

Urinalysis: Appearance, Blood, Color, Glucose, Leukocyte esterase, pH, Protein, Urobilinogen. Reflex to microscopic urinalysis if dipstick result is abnormal. At each visit this is tested, it will be recorded whether female subjects of childbearing potential are currently menstruating.

6.7.2. Medical History

Medical history including details regarding illnesses and allergies, date(s) of onset, and whether condition(s) is currently ongoing, and medication history, including prior HCV treatment history if available will be collected on all subjects during screening.

6.7.3. Complete Physical Examination

A complete physical examination must include source documentation of general appearance, and the following body systems: Head, neck and thyroid; eyes, ears, nose, throat, mouth and tongue; chest (excluding breasts); respiratory; cardiovascular; lymph nodes, abdomen; skin, hair, nails; musculoskeletal; neurological.

6.7.4. Vital Signs

Assessment of vital signs will include measurement of resting blood pressure, pulse, respiratory rate, and temperature.

Blood pressure will be measured using the following standardized process:

- Subject should sit for ≥ 5 minutes with feet flat on the floor and measurement arm supported so that the midpoint of the manometer cuff is at heart level;
- Use a mercury sphygmomanometer or automatic blood pressure device with an appropriately sized cuff with the bladder centered over the brachial artery;
- Measure and record the blood pressure to the nearest 2 mmHg mark on the manometer or to the nearest whole number on an automatic device.

6.7.5. Creatinine Clearance

Creatinine clearance will be calculated at all visits where blood is drawn. Creatinine clearance is calculated by the Cockcroft-Gault equation {[Cockcroft et al 1976](#)} using actual body weight (BW).

$$\text{Male: } CL_{cr} \text{ (mL/min)} = \frac{[140 - \text{age (years)}] \times \text{BW(kg)}}{72 \times S_{cr}}$$

$$\text{Female: } CL_{cr} \text{ (mL/min)} = \frac{[140 - \text{age (years)}] \times \text{BW(kg)} \times 0.85}{72 \times S_{cr}}$$

S_{cr} = serum creatinine (mg/dL)

6.7.6. 12-Lead ECGs

Subjects will be required to rest in a supine position for ≥ 5 minutes prior to making a recording.

The investigator (or qualified designee) should review the ECG traces recorded in real time for clinically significant abnormalities. On treatment ECGs should be compared to the subject's baseline as part of routine safety monitoring.

6.7.7. HCV Viral RNA Sequencing / Phenotyping Sample (Archive)

Plasma samples will be collected at Baseline/Day 1 and each subsequent visit for HCV viral sequence analysis. At any unscheduled visit initiated for the purpose of confirming HCV virologic breakthrough, a HCV viral sequence/phenotype plasma sample must also be collected. Unused samples may be archived.

Details regarding the collection, processing, and shipping of samples will be included in the lab manual.

6.7.8. HIV Viral RNA Genotyping/Phenotyping Sample (Archive)

Plasma samples will be collected at Baseline/Day 1 and each subsequent visit for HIV viral sequence analysis. At any unscheduled visit initiated for the purpose of confirming HIV virologic failure, an HIV genotype/phenotype plasma sample must also be collected. Unused samples may be archived.

Details regarding the collection, processing, and shipping of samples will be included in the lab manual.

6.7.9. Single Pharmacokinetic (PK) Sample

Single PK blood samples will be collected for all subjects at each on-treatment visit and archived for PK analysis of SOF (and metabolites), and VEL.

Details regarding the collection, processing, and shipping of samples will be included in the lab manual.

6.7.10. Pharmacogenomics Testing

An additional and distinct informed consent document will be provided to allow the Sponsor to obtain and test a subject's blood sample taken on Baseline/Day 1 for pharmacogenomics discovery research. If not obtained at Baseline/Day 1, the sample may be drawn at any time during the study. PPD

6.7.11. Sample Storage

PPD

6.7.12. Pregnancy Testing

All females of childbearing potential will have urine pregnancy testing every 4 weeks during the dosing period and 30 days after last dose of SOF/VEL, 6 months after the last dose of RBV, or last visit of the study, whichever comes last.

If a positive urine pregnancy test is reported, an immediate confirmation with Serum β -hCG is required.

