3.5. Discontinuations

If the subject meets the Virologic Response-Based Stopping Criteria (Section 3.3.1), they should complete an Early Termination Visit as soon as possible after SOF/VEL is discontinued and complete post-treatment visits up to 30 days after the last dose of SOF/VEL and/or 60 days after the last dose of RBV to assess for safety.

If the subject meets the Stopping Rules for Individual Subjects (Section 3.4) or other criteria for discontinuation of study treatment (Section 3.7), prior to completion of SOF/VEL dosing period, the subject should complete an Early Termination Visit as soon as possible after SOF/VEL is discontinued and complete the post-treatment assessments as described in Section 6.3 and in Study Procedures [Appendix 2](#).

Subjects discontinuing treatment prior to completion of dosing period for reasons other than those described in Sections 3.3, 3.4 and 3.7 should complete an Early Termination Visit as soon

as possible after SOF/VEL is discontinued. The subject should also complete the post-treatment assessments as described in Section 6.3 and in Study Procedures Appendix 2.

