6.4. Posttreatment Assessments

The post-treatment Week 4 and 12 visits should be timed from the date of last administration of study drug. All subjects must complete the post-treatment Week 4 visit. All subjects who achieve SVR4 will attend the Week 12 visit. The end of study will occur at the post-treatment Week 4 visit in the case of subjects who do not achieve SVR4, and the post-treatment Week 12 visit in the case of patients who do achieve SVR4.

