8.2.2. Assessment of Severity

The severity grading of AEs will be assessed as Grade 1, 2, 3, or 4 using the GSI Grading Scale for Severity of Adverse Events and Laboratory Abnormalities ([Appendix 3](#)). For AEs associated with laboratory abnormalities, the event should be graded on the basis of the clinical severity in the context of the underlying conditions; this may or may not be in agreement with the grading of the laboratory abnormality.

8.3. Investigator Requirements and Instructions for Reporting Adverse Events and Serious Adverse Events to Gilead

Requirements for collection prior to study drug initiation:

- After informed consent, but prior to initiation of study medication, the following types of events should be reported on the case report form (eCRF): all SAEs and adverse events related to protocol-mandated procedures.

Adverse Events

- Following initiation of study medication, all AEs, regardless of cause or relationship, pregnancy and other special situation reports, until 30 days after last administration of study drug must be collected/ reported to the eCRF database as instructed.
- All AEs should be followed up until resolution or until the adverse event is stable, if possible. Gilead Sciences may request that certain AEs be followed beyond the protocol defined follow up period.

Serious Adverse Events

- All SAEs, regardless of cause or relationship, that occurs after the subject first consents to participate in the study (ie, signing the informed consent) and throughout the duration of the study, including the protocol-required post-treatment follow-up period, must be reported to the eCRF database and Gilead Drug Safety and Public Health (DSPH) as instructed. This also includes any SAEs resulting from protocol-associated procedures performed after informed consent is signed.

- Any SAEs and deaths that occur after the post-treatment follow-up visit but within 30 days of the last dose of study drug, regardless of causality, should also be reported.
- Investigators are not obligated to actively seek SAEs after the protocol defined follow up period, however, if the investigator learns of any SAEs that occur after study participation has concluded and the event is deemed relevant to the use of IMP, he/she should promptly document and report the event to Gilead DSPH.
- All AEs and SAEs will be recorded in the eCRF database within the timelines outlined in the eCRF completion guideline.

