 - Transdermal contraceptive patch
 - Contraceptive vaginal ring

Female subjects must also refrain from egg donation and in vitro fertilization during study treatment and until at least 30 days after the last dose of SOF/VEL or 6 months after the last dose of RBV, whichever occurs last.

5) Contraception Requirements for Male Subjects

During the study, male subjects with female partners of childbearing potential should use condoms until 30 days after the last dose of SOF/VEL treatment or 7 months after the last dose of RBV, whichever comes last, when engaging in intercourse of reproductive potential. If their female partner is of childbearing potential (as defined above), their female partner must use 1 of the methods of birth control listed above from the date of Screening until 30 days after the last dose of SOF/VEL or 7 months after last dose of RBV, whichever comes last.

Male subjects must also refrain from sperm donation during treatment and until at least 30 days after the last dose of SOF/VEL or 7 months after the last dose of RBV, whichever comes last.

6) Unacceptable Birth Control Methods

Birth control methods that are unacceptable include periodic abstinence (e.g., calendar, ovulation, symptothermal, post-ovulation methods), withdrawal (coitus interruptus), spermicides only, and lactational amenorrhea method (LAM). Female condom and male condom should not be used together.

7) Procedures to be Followed in the Event of Pregnancy

Subjects will be instructed to notify the investigator if they become pregnant at any time during the study, if they become pregnant within 30 days of last dose of SOF/VEL, or if they become pregnant within 6 months of the last dose of RBV. Subjects who become pregnant or who suspect that they are pregnant during the study must report the information to the investigator and discontinue study drug immediately. Subjects whose partner has become pregnant or suspects she is pregnant within 30 days of the last dose of SOF/VEL or 7 months after the last dose of RBV, whichever occurs last, must report the information to the investigator.

Instructions for reporting pregnancy, partner pregnancy, and pregnancy outcome are outlined in Section [8.5.1.1](#)

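### Ribavirin follow-up required by Protocol 6.7.12 and 3.5 falls after the last scheduled visit, and the pregnancy-reporting periods disagree

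*Protocol*

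**What the plan says.** **Testing.** Protocol 6.7.12 has females of childbearing potential tested every 4 weeks on treatment and then to the latest of three dates: 30 days after SOF/VEL, "6 months after the last dose of RBV, or last visit of the study, whichever comes last".

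**End of study.** Protocol 6.6 states: "The end of study will occur at the post-treatment Week 4 visit in the case of subjects who do not achieve SVR4". Section 6.4 sets it at "the post-treatment Week 12 visit in the case of patients who do achieve SVR4". A subject with quantifiable HCV RNA at either visit "will be asked to return for confirmatory visit within 2 weeks" (6.5). The last column of Appendix 2 is post-treatment Week 12, and the schedule in SAP Appendix 2 stops there too.

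**Safety follow-up after virologic stopping.** For subjects who meet the criteria in 3.3.1, Protocol 3.5 asks for post-treatment visits "up to 30 days after the last dose of SOF/VEL and/or 60 days after the last dose of RBV to assess for safety".

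**Pregnancy reporting.** Three periods are given:
- Section 8.3: "pregnancy and other special situation reports, until 30 days after last administration of study drug must be collected".
- Section 8.5.1.1: from the start of study medication throughout the study, including follow-up after study drug. It also covers partner pregnancies and outcomes that occur after the study has ended.
- Appendix 5, item 7: subjects notify the investigator "if they become pregnant within 6 months of the last dose of RBV", with 7 months for partners of male subjects.

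**The concern.** The protocol itself calls ribavirin a known teratogen that is cleared slowly, and asks for extreme care to avoid pregnancy for up to 6 months after treatment (Section 1.3 and Appendix 5). Only Group 2 receives it. The testing rule follows from that risk, but the visit schedule stops well short of it. A site working from Section 6 and Appendix 2 would do the last pregnancy test at post-treatment Week 4 or Week 12 and close the subject out. The 6-month test would then be omitted or become a predictable deviation.

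The same kind of mismatch affects the 60-day rule. On reporting, a site that learns of a pregnancy several months after the last dose finds three different periods and no statement of which governs. SAP 7.7 lists only pregnancies during the study, so such a case also has no clear place in the outputs.

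**Working it through.** The plan gives no figure to reproduce. The check is calendar arithmetic in days after the last dose.

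**Inputs.**
- Post-treatment Week 4 = day 28 and Week 12 = day 84, each ± 5 days (6.4.1, 6.4.2), timed from the last dose of study drug (6.4).
- Confirmatory visit: at most 14 days later (6.5).
- Required follow-up: 6 months after ribavirin (6.7.12) and 60 days after ribavirin (3.5).
- Assumptions: 6 months is 182 to 184 days; both drugs stop on the same day; 6.7.12 is read in its least demanding sense, as one test at 6 months.

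**Formula.** Gap = required day − day of last visit.

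| Last visit | Day | Gap to 6 months | Gap to day 60 |
|---|---|---|---|
| Week 4, nominal | 28 | 182 − 28 = 154 to 184 − 28 = 156 | 60 − 28 = 32 |
| Week 4, latest | 28 + 5 = 33 | 149 to 151 | 27 |
| Week 4, latest, plus confirmatory visit | 33 + 14 = 47 | 135 to 137 | 13 |
| Week 12, nominal | 84 | 98 to 100 | covered |
| Week 12, latest | 84 + 5 = 89 | 93 to 95 | covered |
| Week 12, latest, plus confirmatory visit | 89 + 14 = 103 | 79 to 81 | covered |

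The 6-month test is therefore 135 to 156 days past the last visit without SVR4, and 79 to 100 days past it with SVR4. A visit at the early edge of its window adds up to 5 days.

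**Ribavirin stopped early.** Suppose ribavirin stops on study day r and SOF/VEL runs to day 84. The Week 12 post-treatment visit is then on study day 84 + 84 = 168, at the latest 173. The 6-month point is r + 182. Even with r = 1 it is day 183, still after that visit. Only a confirmatory visit at its latest (173 + 14 = 187) could reach it, and only with r of 5 or less.

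The 60-day gap behaves differently. If ribavirin stops d days before SOF/VEL, the gap to a nominal Week 4 visit is 60 − d − 28, which closes once d is 32 or more.

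**Against the 30-day period in 8.3.** Day 60 lies 60 − 30 = 30 days beyond it. Month 6 lies 182 − 30 = 152 to 184 − 30 = 154 days beyond it.

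**Who is affected.** The 6-month test concerns Group 2 females of childbearing potential; their number is not stated. The 60-day rule concerns ribavirin-treated subjects who meet the on-treatment criteria in 3.3.1. The protocol's background suggests few of these: in the ASTRAL-3 study 0 of 277 SOF/VEL subjects had on-treatment virologic failure (Section 1.2.2.1.3), and in ASTRAL-4 1 of 87 SOF/VEL + RBV subjects discontinued for virologic failure (Section 1.2.2.1.4). If those rates carried over, 0 to about 1 (100 × 1/87 = 1.1) of 100 Group 2 subjects would be affected. The populations differ, so this is only an indication.

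**The case against.** Four points can be made on the other side.

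1. **The testing is not impossible.** A reader might infer that the 6-month test cannot be carried out at all. The documents do not go that far. Section 6.7.12 itself contemplates a date later than the last visit, and 6.3.5 allows unscheduled visits when the sponsor or investigator asks. But neither section sets up such a visit for this purpose, and the defined end of study has already passed. What stands is that the test is required and not scheduled.

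2. **Later pregnancies are not simply left unreported.** A reader of 8.3 alone might conclude that pregnancies after day 30 go unreported. Section 8.5.1.1 and Appendix 5 both reach further, and SAEs are collected throughout post-treatment follow-up. The fault is a conflict between sections.

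3. **The 60-day rule is narrow.** It might be taken to cover every virologic failure in Group 2. Section 3.5 ties it to the on-treatment criteria in 3.3.1, so subjects who relapse after treatment are outside it. A subject who meets those criteria but has HCV RNA below LLOQ at post-treatment Week 4 continues to Week 12, which covers day 60. The phrase could also be read as a ceiling on visits rather than a required date. On that reading the 60-day clause adds almost nothing, because the only visit the schedule offers these subjects after Week 4 is the confirmatory one.

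4. **No planned estimate changes.** Treatment-emergent safety is defined to last dose plus 30 days, pregnancy is not itself an AE, and SAP 7.7 provides only a listing. This is correct, and it limits the point to subject protection and completeness of safety follow-up.

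The consent pages are not available for review, so any arrangement described only there cannot be checked.

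**Conclusion.** The contradiction is in the protocol's own text. The 6-month pregnancy test has no scheduled visit, and no allowance for visit windows or confirmatory visits closes the gap when both drugs stop together. The 60-day safety follow-up has a smaller gap, limited to subjects who meet the on-treatment stopping criteria and end the study at Week 4; it can close if ribavirin stopped well before SOF/VEL. The three pregnancy-reporting periods do not agree.

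The sizes rest on 6 months being 182 to 184 days and on a common last-dose date. SVR12, its confidence intervals and the sample size are unaffected. The matter should be corrected because it concerns a safety test that the protocol itself requires, in the only arm given ribavirin.

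**What to change.** Reconcile Protocol 3.5, 6.4, 6.6, 6.7.12, 8.3, 8.5.1.1 and Appendices 2 and 5 so that all of them give the same end date for each of three things: ribavirin pregnancy testing, pregnancy reporting, and safety follow-up after virologic stopping. Appendix 2 should show how any assessment after the last clinic visit is obtained. No particular duration is proposed here; that is for the sponsor to settle.

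If collection will run past post-treatment Week 12, SAP 7.7 should say whether later pregnancies are listed. SAP 2.2 should say how they relate to a final analysis triggered by completion of the Week 12 visit.

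The cost is protocol wording and, if the longer periods are kept, a small number of post-study assessments in Group 2 that 6.7.12 and 3.5 already require.

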7. TOXICITY MANAGEMENT

7.1. Dose Modification Due to Toxicity

7.2. Group 1: Subjects administered SOF/VEL

There is no option for dose reduction or modification of SOF/VEL

7.3. Group 2: Subjects administered SOF/VEL+ RBV

Dose modification for subjects administered SOF/VEL+RBV should be performed according to the prescribing information.

Dose reduction of SOF/VEL is not permitted.

Table 7-1. Ribavirin Dose Modification Guideline for Coadministration with SOVALDI

Laboratory Values	Reduce Ribavirin Dose to 600 mg/day ^a If:	Discontinue Ribavirin If: ^b
Hemoglobin in patients with no cardiac disease	<10 g/dL	<8.5 g/dL
Hemoglobin in patients with history of stable cardiac disease	≥2 g/dL decrease in hemoglobin during any 4 week treatment period	<12 g/dL despite 4 weeks at reduced dose

a The daily dose of ribavirin is administered orally in two divided doses with food.

b Once ribavirin has been withheld due to either a laboratory abnormality or clinical manifestation, an attempt may be made to restart ribavirin at 600 mg daily and further increase the dose to 800 mg daily. However, it is not recommended that ribavirin be increased to the original assigned dose (1000 mg to 1200 mg daily).

If RBV is permanently discontinued, SOF should also be discontinued.

7.3.1. Subject Stopping Rules

See Section 3.4 for individual subject stopping rules..

7.4. Subject Stopping Rules

See Section 3.4 for individual subject stopping rules.

7.5. Special Situations Reports

7.5.1. Definitions of Special Situations

Special situation reports include all reports of medication error, abuse, misuse, overdose, reports of adverse events associated with product complaints, and pregnancy reports regardless of an associated AE.

Medication error is any unintentional error in the prescribing, dispensing, or administration of a medicinal product while in the control of the health care provider, subject, or consumer.

Abuse is defined as persistent or sporadic intentional excessive use of a medicinal product by a subject.

Misuse is defined as any intentional and inappropriate use of a medicinal product that is not in accordance with the protocol instructions or the local prescribing information.

An overdose is defined as an accidental or intentional administration of a quantity of a medicinal product given per administration or cumulatively which is above the maximum recommended dose as per protocol or in the product labelling (as it applies to the daily dose of the subject in question). In cases of a discrepancy in drug accountability, overdose will be established only when it is clear that the subject has taken the excess dose(s). Overdose cannot be established when the subject cannot account for the discrepancy except in cases in which the investigator has reason to suspect that the subject has taken the additional dose(s).

Product complaint is defined as complaints arising from potential deviations in the manufacture, packaging, or distribution of the medicinal product.

